10.2. Populations for analyses

For purposes of analysis, the following analysis sets are defined:

Analysis Set	Description
Enrolled	All subjects who sign informed consent
Exposed	All subjects who received at least 1 dose of the study treatment. The allocation in a group is done in function of the administered treatment.
Full Analysis	All subjects who received at least 1 dose of the study treatment and have post-vaccination immunogenicity data
Per Protocol	All subjects who received at least 1 dose of the study treatment to which they are randomized and have post-vaccination data (Full Analysis Set) minus subjects with protocol deviations that lead to exclusion

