
To demonstrate the non-inferiority of the antibody response to rMenB+OMV NZ given concomitantly with MenACWY to healthy subjects 16-18 years of age compared to rMenB+OMV NZ administered alone, as measured by serum bactericidal assay using human complement (hSBA) Geometric Mean Titers (GMTs) against N. meningitidis serogroup B indicator strains M14459 (fHbp), 96217 (NadA), NZ98/254 (PorA) and M07-0241084 (NHBA), at one month after the second vaccination with rMenB+OMV NZ.
 
Criterion: Non-inferiority will be demonstrated if for each of the four serogroup B test strains, the lower limit of the 2-sided 95% confidence interval of the between-group ratio of hSBA GMTs (rMenB+OMV NZ with MenACWY versus rMenB+OMV NZ alone) is >0.5.
	
Co-primary endpoints for Group MenB+MenACWY and Group MenB are the hSBA GMTs for rMenB+OMV NZ against each of the four serogroup B test strains (M14459, 96217, NZ98/254 and M07-0241084) at one month after the second vaccination with rMenB+OMV NZ (Visit 4, Month 3).

CONFIDENTIAL

205419 (MENB REC 2ND GEN-045 (V72_79))

Statistical Analysis Plan Amendment 3

Objectives	Endpoints

To demonstrate the non-inferiority of the antibody response to MenACWY given concomitantly with rMenB+OMV NZ to healthy subjects 16-18 years of age compared to MenACWY administered alone, as measured by hSBA GMTs against each of the N. meningitidis serogroups A, C, W and Y, at one month after the (study) vaccination with MenACWY.
 
Criterion: Non-inferiority will be demonstrated if for each of the four serogroups A, C, W and Y, the lower limit of the 2-sided 95% confidence interval of the between-group ratio of hSBA GMTs (rMenB+OMV NZ with MenACWY versus MenACWY alone) is >0.5.
	
Co-primary endpoints for Group MenB+MenACWY and Group MenACWY are the hSBA GMTs against each of the four serogroups A, C, W and Y with MenACWY at one month after the study vaccination of MenACWY (Visit 2, Month 1).

Secondary	

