3. STUDY DESIGN

Protocol waivers or exemptions are not allowed unless necessary for the management of immediate safety concerns. Therefore, adherence to the study design requirements, are essential and required for study conduct.

Approximately 945 subjects will be screened to achieve 750 evaluable subjects for an estimated total of 250 evaluable subjects per treatment group. Withdrawals will not be replaced.

- Type of study: self-contained
- Experimental design: Phase IIIB, observer-blind, randomised, controlled, multi-centric, study with 3 parallel groups.
- Duration of the study:
 - Epoch 001: Primary starting at Visit 1 (Day 1) and ending at Visit 4 (Day 91)
 - Epoch 002: Safety follow-up period starting at Visit 4 (Day 91) and ending at Study termination-call (Day 451 [Month 15] or Day 271 [Month 9] for subjects who have not reached Day 271 at the time Protocol Amendment 7 takes effect)
- Primary Completion Date (PCD): Study termination-call (Day 451 [Month 15] or Day 271 [Month 9] for subjects who have not reached Day 271 at the time Protocol Amendment 7 takes effect)
- End of Study (EoS): Last subject last visit (LSLV) [last concluding contact on Day 451 (Month 15) or Day 271 (Month 9) for subjects who have not reached Day 271 at the time Protocol Amendment 7 takes effect] or Date of the last testing/reading released of the Human Biological Samples or imaging data, related to primary and

CONFIDENTIAL

205419 (MENB REC 2ND GEN-045 (V72_79))

Statistical Analysis Plan Amendment 3

secondary endpoints, whichever occurs later. EoS must be achieved no later than 8 months after LSLV. EoS cannot be before LSLV.

- Study groups:
 - Group MenB+MenACWY: rMenB+OMV NZ given concomitantly with MenACWY at study Day 1; rMenB+OMV NZ at study Day 61; Placebo at study Day 91.
 - Group MenB: rMenB+OMV NZ given concomitantly with Placebo at study Day 1 and rMenB+OMV NZ at study Day 61; MenACWY at study Day 91.
 - Group MenACWY: MenACWY given concomitantly with Placebo at study Day 1; rMenB+OMV NZ at study Day 61 and at study Day 91.

Table 1 Study groups, treatment and epochs foreseen in the study

Study Groups	Number of subjects	Age (Min-Max)	Treatment name	Vaccine/Product name	Epochs (Blinding)	
					Epoch 001 (observer-blind)	Epoch 002 (observer-blind)
MenB+MenACWY	315	16 years – 18 years	Bexsero	rMenB+OMV NZ	x	x
			Menveo	MenACWY (MenA lyo+MenCWY liquid		
			Placebo	NaCl		
MenB	315	16 years – 18 years	Bexsero	rMenB+OMV NZ	x	x

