4.4. Per Protocol Set

All subjects who received at least one dose of the study treatment to which they are randomised and have post-vaccination data (Full Analysis Set) minus subjects with protocol deviations that lead to exclusion. PDs leading to a Per Protocol Set exclusion are detailed in Section 4.5.2.

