4.5.2. Elimination from Per-protocol analysis Set (PPS) and Full Analysis Set (FAS)

4.5.2.1. Excluded subjects

A subject will be excluded from the analysis under the following conditions

Table 4 Exclusion codes

Code	Condition under which the code is used	Visit (timepoints) where the code is applicable	Applicable for analysis set/endpoint
800	Fraudulent data	All	All
900	Invalid informed consent	All	All
1030	Study vaccine not administered at all	Visits 1, 3 and 4	All
1040	Administration of concomitant vaccine(s) forbidden in the protocol	Visit 1, 2 (before BS at M1)	PPS M1 and M3
1040	Administration of concomitant vaccine(s) forbidden in the protocol	Visit 2 (after BS at M1), 3, 4 (before BS at M3)	PPS M3
1050	Randomisation failure	Visit 1	PPS M1 and M3
1060	Randomisation code was broken	All	PPS M1 and M3
1070	Subjects got vaccinated with the correct vaccine but containing a lower volume	Visit 1	PPS M1

CONFIDENTIAL

205419 (MENB REC 2ND GEN-045 (V72_79))

Statistical Analysis Plan Amendment 3

Code	Condition under which the code is used	Visit (timepoints) where the code is applicable	Applicable for analysis set/endpoint
1070	Subjects got vaccinated with the correct vaccine but containing a lower volume	Visit 3	PPS M3
1070	Vaccination not according to protocol	Visit 1	PPS M1
1070	Vaccination not according to protocol	Visit 3	PPS M3
1080	Vaccine temperature deviation	Visit 1	PPS M1
1080	Vaccine temperature deviation	Visit 3	PPS M3
1090	Expired vaccine administered	Visit 1	PPS M1
1090	Expired vaccine administered	Visit 3	PPS M3
2010	Protocol violation (inclusion/exclusion criteria)	All	PPS M1 and M3
2040	Administration of any medication forbidden by the protocol	Visit 1, 2 (before BS at M1)	PPS M1 and M3
2040	Administration of any medication forbidden by the protocol	Visit 2 (after BS at M1), 3, 4 (before BS at M3)	PPS M3
2050	Not withdrawn after developing withdrawal criteria other than prohibited concomitant vaccination/medication (medical condition forbidden)	All	PPS M1 and M3
2060	Concomitant infection related to the vaccine which may influence immune response (only meningococcal infection)	All	PPS M1 and M3
2080	Subjects did not comply with vaccination schedule	Visit 1	PPS M1
2080	Subjects did not comply with vaccination schedule	Visit 3	PPS M3
2090	Subjects did not comply with blood sample schedule	Visit 2	PPS M1
2090	Subjects did not comply with blood sample schedule	Visit 4	PPS M3

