2100	Serological results not available post-vaccination for any of the four N. meningitidis serogroup B indicator strains	Visit 2	FAS and PPS M1 (secondary objective)
2100	Serological results not available post-vaccination for any of the four N. meningitidis serogroup B indicator strains	Visit 4	FAS and PPS M3 (primary objective)

CONFIDENTIAL

205419 (MENB REC 2ND GEN-045 (V72_79))

Statistical Analysis Plan Amendment 3

Code	Condition under which the code is used	Visit (timepoints) where the code is applicable	Applicable for analysis set/endpoint
2100	Serological results not available post-vaccination for any of the N. meningitidis serogroups A, C, W and Y (hSBA)	Visit 2	FAS and PPS M1 (primary objective)
2100	Serological results not available post-vaccination for any of the N. meningitidis serogroups A, C, W and Y (ELISA)	Visit 2	FAS and PPS M1 (secondary objective)
2120	Obvious incoherence or abnormality or error in data for any of the four N. meningitidis serogroup B indicator strains	Visit 2	FAS and PPS M1 (secondary objective)
2120	Obvious incoherence or abnormality or error in data for any of the four N. meningitidis serogroup B indicator strains	Visit 4	FAS and PPS M3 (primary endpoint)
2120	Obvious incoherence or abnormality or error in data for any of the N. meningitidis serogroups A, C, W and Y (hSBA)	Visit 2	FAS and PPS M1 (primary endpoint)
2120	Obvious incoherence or abnormality or error in data for any of the N. meningitidis serogroups A, C, W and Y (ELISA)	Visit 2	FAS and PPS M1 (secondary objective)
2130	Subject bled despite it was not planned to be bled	All	PPS M1 and M3
2170	Pregnancy	Visit 1	PPS M1 and M3
2170	Pregnancy	Visit 3	PPS M3

M1 and M3: months of the study schedule at which the subject will be eliminated from a specific population, i.e., Day 31 and Day 91.

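### A faulty Visit 1 injection removes a subject from the Month 1 per-protocol set but not from the Month 3 set that tests the two-dose MenB co-primary

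*SAP*

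**What the plan says.** Protocol 10.2 defines the per-protocol set as the full analysis set "minus subjects with protocol deviations that lead to exclusion" and does not list the deviations. SAP 4.4 repeats this and adds: "PDs leading to a Per Protocol Set exclusion are detailed in Section 4.5.2". Table 4 in SAP 4.5.2.1 is therefore the only operative rule.

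Table 4 works with two time-specific sets, PPS M1 and PPS M3. Its footnote explains the labels as "months of the study schedule at which the subject will be eliminated from a specific population", that is Day 31 and Day 91. Code 1070 has two wordings, one for a lower volume and one for "Vaccination not according to protocol". Code 1080 is a temperature deviation and code 1090 is expired vaccine. For all four, the Visit 1 row is marked PPS M1 and the Visit 3 row PPS M3.

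Other codes are marked differently. "Administration of concomitant vaccine(s) forbidden in the protocol" (code 1040), when it happens at Visit 1 or before the Month 1 sample at Visit 2, is marked for both sets.

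The MenB co-primary is measured "at one month after the second vaccination with rMenB+OMV NZ (Visit 4, Month 3"), and Table 4 ties the Visit 4 MenB serology to "FAS and PPS M3 (primary objective"). SAP 3 gives the co-administration arm as "rMenB+OMV NZ given concomitantly with MenACWY at study Day 1; rMenB+OMV NZ at study Day 61".

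**The concern.** For the MenB comparison, Visit 1 supplies the first of the two rMenB+OMV NZ doses. In the combined arm it also supplies the only MenACWY co-administration, which is the exposure being tested. A per-protocol set for that comparison should hold subjects who received both as planned. Under Table 4 a subject whose Visit 1 injection was low in volume, mis-prepared, temperature-deviated or expired leaves the Month 1 set and stays in the Month 3 set.

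SAP 5.4.1.1 makes the PPS the primary set for non-inferiority, with the full analysis set (FAS) as support. The FAS also keeps these subjects (SAP 4.3), so neither planned analysis gives a MenB result free of them.

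The direction of bias depends on the fault:

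- Weakened MenACWY in the combined arm reduces any interference and favours non-inferiority.
- A defective first rMenB dose in Group MenB also favours non-inferiority.
- A defective first rMenB dose in the combined arm works against it.
- Equal faults in both arms leave the ratio unchanged.

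**Working it through.** **Step 1. Table 4, rows side by side**

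| Code | Visit covered | Set marked |
|---|---|---|
| 1070 (both wordings), 1080, 1090 | Visit 1 | M1 only |
| 1070 (both wordings), 1080, 1090 | Visit 3 | M3 only |
| 1040, 2040 | Visit 1, and Visit 2 before the M1 sample | M1 and M3 |
| 1040, 2040 | after the M1 sample, up to the M3 sample | M3 only |
| 1050 | Visit 1 | M1 and M3 |
| 2170 | Visit 1 | M1 and M3 |
| 2170 | Visit 3 | M3 only |

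If an M1 mark meant Month 1 onwards, the explicit M1-and-M3 marks would be redundant. The footnote and SAP 4.4 contain no carry-forward rule, and the basic PPS definition asks for only one dose of the randomised treatment. No other row catches a faulty Visit 1 injection at Month 3.

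**Step 2. Reproduce the plan's power**

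Inputs from Protocol 10.1.2:
- upper-limit SDs (Table 19) of 0.72443 (M14459), 0.30774 (96217), 0.62129 (NZ98/254) and 0.61171 (M07-0241084);
- margin 0.5, true ratio 0.9, 250 per arm, and joint power as the product over strains.

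Per strain, power comes from the noncentral t distribution with df = 2n − 2 and ncp = log10(ratio/0.5) / (SD·√(2/n)). With log10(0.9/0.5) = 0.2553 the powers are 97.57%, 100%, 99.57% and 99.65%. The product is 96.81%, as in protocol Table 20.

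**Step 3. Bias towards non-inferiority**

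The documents give no fault rate, so the rates and effects in steps 3 to 5 are assumptions. Let the true ratio be 0.5, and let a share f of the combined arm have a weakened MenACWY injection and a ratio r to the control arm. The errors described in Protocol 3.3.1 still deliver part of the vaccine, so r = 0.6 or 0.7 is used as a partial effect.

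One-sided error = 1 − Φ(1.96 − f·log10(r/0.5)/SE), with SE = SD·√(2/250). SE is 0.0648 for M14459 and 0.0275 for 96217, the strains with the largest and smallest SD.

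| r | f | M14459 | 96217 |
|---|---|---|---|
| 0.7 | 1% | 2.6% | 2.8% |
| 0.7 | 2% | 2.8% | 3.2% |
| 0.6 | 1% | 2.6% | 2.7% |
| 0.6 | 2% | 2.6% | 2.9% |

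The nominal value is 2.5%, and the other two strains lie between these columns. In the extreme case of wholly ineffective MenACWY (r = 1), the range over strains is 2.8–3.2% at f = 1% and 3.1–4.1% at f = 2%.

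**Step 4. Bias against non-inferiority**

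Let the true ratio be 0.9, and let a defective first rMenB dose multiply the titre by k in a share f of the combined arm. The apparent ratio is 0.9·k^f.

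| k | f | Apparent ratio | Joint power |
|---|---|---|---|
| 0.5 | 1% | 0.894 | 96.40% |
| 0.5 | 2% | 0.888 | 95.95% |
| 0.7 | 1% | 0.897 | 96.60% |
| 0.7 | 2% | 0.894 | 96.39% |

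**Step 5. Cost of removing the subjects**

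Each subject in the two compared arms gets two Visit 1 injections. At an assumed equal fault rate q per injection, the share removed is 1 − (1 − q)². That is 1.0% at q = 0.5% and 2.0% at q = 1%, or 2.5 and 5 of 250. At a true ratio of 0.9, joint power is 96.60% with 247 per arm and 96.46% with 245 per arm.

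**The case against.** The strongest reply is that the table is not careless. Every dose-delivery code (1070, 1080, 1090 and also 2080) ties a Visit 1 deviation to the next sample and a Visit 3 deviation to the one after. Codes 1050 and 2170 concern the subject rather than the dose, so they are looser comparators. This stands as a description. It does not justify the rule for an endpoint that depends on both doses, and the SAP gives no rationale. Code 2080 is less exposed, because its Visit 3 row can catch a wrong dose interval. Codes 1040 and 2040 remain fair comparators.

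Second, the codes are broader than a defective dose. The second wording of 1070 is undefined and could cover a wrong arm. Protocol 7.4.1 allows vaccine affected by a temperature excursion to be cleared for use. Both points are true, but the SAP already treats these codes as disqualifying at Month 1.

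Third, the effect is small. Protocol 7.4.1 calls for quarantine and an expiry check. The error figures need a true ratio at the margin and faults in one arm only, and success requires all four strains. On power, correcting the rule gains only 0 to about 0.5 points: 96.60% either way at 1% faults with a 30% titre loss, and 95.95% against 96.46% at 2% with halved titres. This stands. The case for the change is what the primary set is meant to contain, not power.

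Fourth, excluding Group MenB subjects for a faulty placebo has no biological basis, and reconstitution errors arise with MenACWY and not with saline, so a uniform rule need not balance exclusions exactly. That is fair. However, the codes already make no distinction by component at Month 1. At equal fault rates of 0.5–1% per injection, a placebo exception would remove 0.5–1% from Group MenB against 1–2% from the combined arm.

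**Conclusion.** The concern holds. For codes 1070 (both wordings), 1080 and 1090, Table 4 keeps subjects with a faulty Visit 1 injection in the Month 3 per-protocol set, which does not suit a two-dose endpoint. The reading of the table is certain. The size of the consequence is not, because no fault rate is documented.

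With 1–2% affected in one arm, the per-strain one-sided error is 2.6–3.2% under a partial loss of MenACWY effect, and at most 4.1% under total loss. In the opposite direction, joint MenB power falls by 0.2 to 0.9 points. No stated sample size, power figure or success criterion changes. This should be fixed, but it does not threaten the trial.

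The finding does not extend to a Visit 1 injection that was not given at all (code 1030) or to code 2080. It does not claim a contradiction with the protocol's definition of evaluable.

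**What to change.** Before unblinding, change the Visit 1 rows of code 1070 (both wordings), 1080 and 1090 in SAP Table 4 so that they exclude from both PPS M1 and PPS M3. Apply this in the same way in every group and to whichever Visit 1 injection is affected, with no exception for placebo. It affects the Month 3 comparison only in Groups MenB+MenACWY and MenB, because Group MenACWY has no Visit 4 read-out in protocol Table 14.

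If the data are already unblinded, keep the planned PPS as primary and report the corrected Month 3 set as a labelled sensitivity analysis. The documents do not say whether they are; SAP Amendment 3 is dated 03 Jun 2024.

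The cost is four table cells. A few subjects leave the Month 3 PPS and remain in the FAS. At the assumed 1–2% removed per arm, joint MenB power goes from 96.81% to 96.60% or 96.46%, a loss of 0.21 to 0.35 points.

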5. STATISTICAL ANALYSES

That standard data derivation rules and stat methods are described in Section 10.1 while the study specific data derivation rules and stat methods are described in Section 9.

5.1. Demography

5.1.1. Analysis of demographics/baseline characteristics planned in the protocol

Descriptive statistics (mean, standard deviation [SD], median, minimum and maximum) for age, height, weight and body mass index (BMI) at enrolment will be calculated overall and by Group.

Distributions of subjects by sex, race, ethnic origin, geographical locations (US sites, non-US sites) and according to the pre-vaccination hSBA titer (per strain, <LLOQ or \geq LLOQ) will be summarized overall and by Group.

5.1.2. Additional considerations

Potential participants who are screened for the purpose of determining eligibility for the study, but do not participate in the study, are not considered enrolled, see Section 4.1 for enrolled definition, unless otherwise specified by the protocol.

The number of subjects with suspected, probable or confirmed COVID-19 infection will be summarized by treatment arm and across diagnoses. This summary will be provided for the exposed set.

The number of enrolled participants who discontinued the study will be tabulated by group with the reason for discontinuation. The summary table will be produced by relationship to COVID-19.

A summary table of important protocol deviation by relationship (related/not related) to COVID-19 will be provided.

5.2. Exposure

5.2.1. Analysis of exposure planned in the protocol

The frequencies and percentages of subjects with vaccinations will be summarized overall and by vaccine group. Data will be tabulated for the All Enrolled Set.

5.2.2. Additional considerations

NA

5.3. Efficacy/Effectiveness

5.3.1. Analysis of efficacy planned in the protocol

NA

5.3.2. Additional considerations

NA

5.4. Immunogenicity

5.4.1. Analysis of immunogenicity planned in the protocol

5.4.1.1. Primary endpoints

The primary analysis will be conducted using the PPS for the primary (non-inferiority) objective. If, in any study group, the percentage of enrolled or vaccinated subjects with serological results excluded from the per-protocol set for analysis of immunogenicity is 5% or more, a second analysis based on the Full Analysis Set (FAS) will be performed to complement the per-protocol analysis. Supportive analyses using the FAS will also be performed for the primary immunogenicity endpoints.

Within group assessment

- For Group MenB+MenACWY and Group MenB: hSBA GMTs for rMenB+OMV NZ against each of the four serogroup B test strains (M14459, 96217, NZ98/254 and M07-0241084) at one month after the second vaccination for rMenB+OMV NZ (Visit 4) will be calculated.
- For Group MenB+MenACWY and Group MenACWY: hSBA GMTs against each of the four serogroups A, C, W and Y for MenACWY at one month after the study vaccination of MenACWY (Visit 2) will be calculated.

Between group assessment

- The ratio of GMTs between Group MenB+MenACWY versus Group MenB when administered without MenACWY [Group MenB]), at one month after the second vaccination will be calculated.
- The ratio of GMTs between Group MenB+MenACWY versus Group MenACWY when administered alone [Group MenACWY], at one month after the study vaccination of MenACWY will be calculated.

Primary immunogenicity endpoints may be repeated using another panel of strains, if requested.

5.4.1.2. Secondary endpoints

The non-inferiority secondary objective is to be conducted using the PPS.

Within group assessment

- ELISA GMCs against each of the four serogroups A, C, W and Y at one month after the (study) vaccination for groups MenB+MenACWY and MenACWY.

- The percentage of subjects (and 2-sided 95% Clopper-Pearson CIs) with hSBA titers \geq LLOQ for each and all serogroup B test strains after the first and second vaccination for Groups MenB+MenACWY and MenB; and for serogroups A, C, W and Y at one month after the (study) vaccination for Groups MenB+MenACWY and MenACWY.
- hSBA GMTs against each of the four serogroups B test strains at baseline and one month after first vaccination with rMenB+OMV NZ for Groups MenB+MenACWY and MenB.
- GMRs (compared to baseline) against each serogroup B test strains at one month after the first and second vaccination for Groups MenB+MenACWY and MenB and one month after the (study) vaccination for Groups MenB+MenACWY and MenACWY.
- The percentage of subjects (and 2-sided 95% Clopper-Pearson CIs) with fourfold increase in hSBA titers relative to baseline for each serogroup B test strains at one month after the first and the second vaccination for Groups MenB+MenACWY and MenB; and for serogroups A, C, W and Y at one month after the (study) vaccination for Groups MenB+MenACWY and MenACWY.

Between group assessment

- For all four serogroups A, C, W and Y, noninferiority of the responses to MenACWY when given with rMenB+OMV NZ compared to MenACWY administered alone will be assessed in terms of ELISA GMC.
- The ratio of GMTs between Group MenB+MenACWY versus Group MenB when administered alone at one month after the first vaccination, will be calculated.
- Between group differences (Group MenB+MenACWY vs Group MenB and Group MenB+MenACWY vs Group MenACWY), at one month after the first and the second vaccination (as applicable) will be calculated, as well as their associated 95% CIs.

